3.7.3.2 Dose Modifications for MIRV-Related Adverse Events

Table 7 Dose Modifications for MIRV-Related Adverse Events

Severity Grade (CTCAE v5.0)	Dose Modifications for MIRV ^a
HEMATOLOGICAL	
Neutropenia	
Grade 2 and Grade 3	
• Hold drug until ANC is $\geq 1.5 \times 10^9/L$ (1500/μL) and resume at the same dose level
Grade 4	
• Hold drug until ANC is $\geq 1.5 \times 10^9/L$ (1500/μL) and then resume at one lower dose level
Febrile neutropenia Grade 3 or 4 (with single temperature reading $\geq 38.3^{\circ}C$ or a sustained temperature of $> 38^{\circ}C$ for > 1 hour)	
• Hold drug until ANC is $\geq 1.5 \times 10^9/L$ (1500/μL) and then resume at one lower dose level

Severity Grade (CTCAE v5.0)	Dose Modifications for MIRV ^a
Thrombocytopenia	
Grade 2	
 Hold drug until PLT count is $\geq 100 \times 10^9/L$ ($100,000/\mu L$) and dose reduce one dose level
Grade 3	
Grade 3 associated with clinically significant bleeding that requires transfusion therapy	
Grade 4	
Recurrence of Grade 4	
 Permanently discontinue
NON-HEMATOLOGICAL	
Nausea and Vomiting	
Grade 3 (despite use of optimal antiemetics)	Hold drug until resolved to Grade ≤ 1 , then resume at one lower level
Grade 4	Permanently discontinue
Diarrhea	
Grade 3 (despite use of optimal antidiarrheal treatment)	Hold drug until resolved to Grade ≤ 1 , then resume at one lower level
Grade 4	Permanently discontinue
Ocular Disorders	
Noninfectious Pneumonitis	
Infusion-Related Reactions (IRR)	
ALL OTHER NON-HEMATOLOGICAL TOXICITIES (except AEs related to underlying disease, Grade 3 fatigue, isolated symptomatic Grade 3 biochemistry laboratory abnormalities that last for < 7 days including electrolyte abnormalities that respond to medical intervention)	
Grade 3	
Hold drug until resolved to Grade ≤ 1, then resume at one lower level.
 
For any Grade 3 hepatic toxicity that does not resolve to baseline within 7 days, an abdominal CT scan must be performed to assess whether it is related to progressive disease.
 
Grade 3 ALT/AST increase:
 
Hold MIRV until resolved to Grade ≤ 1.
 
 If resolution to Grade ≤ 1 within 7 days, resume at the same dose level. If resolution to Grade ≤ 1 takes more than 7 days, resume MIRV at one dose level lower starting at the next cycle.
\geq Grade 3 cardiac events (excluding Grade 3 hypertension)	Permanently discontinue
Grade 4	Permanently discontinue

Abbreviations: AE = adverse event; ANC = absolute neutrophil count; CT = computed tomography; CTCAE = common terminology criteria for adverse events; MIRV = mirvetuximab soravtansine; PLT = platelets.

- Failure to meet retreatment criteria within 1 cycle (21 days) after the missed dose due to insufficient recovery from a treatment-related toxicity will result in treatment discontinuation unless otherwise specified in the management guidance for a particular toxicity.

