3.7.3 Toxicity Management Guidelines for MIRV

The toxicity management guidelines provided in this section represent general guidance for AEs that are considered by the investigator to be possibly related or related to treatment with MIRV.

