3.7.3.1 MIRV Treatment Criteria

In the absence of an AE that requires dose modification (as specified in the management guidance for a particular toxicity), a subject must meet the following criteria to receive MIRV at any cycle:

- Absolute neutrophil count (ANC) must be $\geq 1.5 \times 10^9/L$ (1,500/ μ L)
- Platelet count must be $\geq 100 \times 10^9/L$ (100,000/ μ L)
- All non-hematologic toxicities for which a causal association to MIRV cannot be ruled out, must be \leq Grade 2 or returned to baseline; the exceptions to this rule being:
 - Treatment-emergent ocular disorders, which must have recovered to Grade < 1 or baseline
 - Treatment emergent pneumonitis which must have recovered to Grade ≤ 1

Dose reductions to be used for AEs that are considered by the investigator to be possibly related or related to treatment with MIRV are described in [Table 6](#).

Table 6 MIRV Dose Reduction Dose Levels

If the subject was receiving MIRV at:	Dose should be reduced to:
6.0 mg/kg AIBW	5.0 mg/kg AIBW
5.0 mg/kg AIBW	4.0 mg/kg AIBW
4.0 mg/kg AIBW	Permanently discontinue

Reduction of MIRV below 4.0 mg/kg will not be permitted. Dose re-escalation is not permitted.

Abbreviations: AIBW = adjusted ideal body weight; MIRV = mirvetuximab soravtansine

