3.7.3.6 Monitoring of Noninfectious Pneumonitis [MIRV Cohort]

Noninfectious pneumonitis has been observed after the administration of MIRV. Noninfectious pneumonitis may result in fatigue, shortness of breath, cough, or respiratory distress.

Drug-induced pneumonitis may be immediately life threatening. If a subject presents with signs or symptoms consistent with pneumonitis and/or other clinically meaningful signs or symptoms of pulmonary toxicity, the subject should be immediately evaluated. Subjects are advised to notify their treating physician immediately if they experience new or worsening shortness of breath, cough, or respiratory distress. Subjects who are asymptomatic may continue dosing of MIRV with close monitoring.

The management and treatment guidelines outlined in [Table 10](#) should be followed.

Table 10 Management of Noninfectious Pneumonitis

CTCAE v5.0 Grade	CTCAE v5.0 Definition	Medical Management of Pneumonitis	Guidelines for Dose Modifications ^a
Grade 1	Asymptomatic; clinical or diagnostic observations only; intervention not indicated	
 Radiologic assessments (CT scan and/or chest x-ray) should be performed as clinically indicated. Monitor for pulmonary symptoms. 	
 Continue dosing in asymptomatic subjects and monitor closely.
Grade 2	Symptomatic; medical intervention indicated; limiting instrumental ADL	
 Radiologic assessments (CT scan and/or chest x-ray) should be performed as clinically indicated. Subject must be evaluated by a pulmonary specialist. Treatment with corticosteroids may be indicated as recommended by a pulmonary specialist and/or institutional guidelines. 	
 Hold dosing until symptoms resolve to Grade \leq 1. MIRV may be resumed at same dose level or one dose level lower after discussion with the Sponsor.
Grade 3	Severe symptoms; limiting self-care		
 Permanently discontinue MIRV.

CTCAE v5.0 Grade	CTCAE v5.0 Definition	Medical Management of Pneumonitis	Guidelines for Dose Modifications ^a

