7.1.1 Events not Qualifying as AEs/SAEs

The following are not considered to be AEs or SAEs:

- Medical or surgical procedures (e.g., endoscopy, appendectomy). The condition that leads to the procedure is considered the AE.
- Elective procedures, planned hospitalizations, and procedures for treatment of conditions noted in the subject's medical history (present prior to signing the ICF) that have not worsened are not considered AEs.
- Situations where an untoward medical occurrence did not occur (i.e., admission to hospital for social circumstances).
- Anticipated day-to-day fluctuations of pre-existing medical conditions that were present at start of study. These conditions are considered part of the subject's medical history and must be adequately documented on the appropriate page of the eCRF.
- Clear progression of disease under study should not be reported as an AE or SAE unless the investigator considers the progression of underlying neoplasia to be atypical in its nature, presentation, or severity from the normal course of the disease in a particular subject. Signs and symptoms that are clearly consistent with the expected progression of the underlying cancer should not be reported as an AE, and hospitalizations due to the progression of cancer do not necessarily qualify for an SAE. Deaths that are clearly determined to be due to disease progression should not be reported as AEs/SAEs.
- In the case where the medical condition is known when the subject enters the trial, only worsening (increased frequency or intensity of the episodes or attacks) will be documented as an AE. If the medical condition is detected during the trial, and if repeated

episodes enable diagnosis of a chronic disease, the episodes will be grouped together in the eCRF, and the diagnosis will be clearly described.

- Laboratory abnormalities: An isolated, out-of-range laboratory result in the absence of any associated clinical finding may or may not be considered an AE; the investigator's evaluation should be based on a consideration of the overall clinical context.

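### Protocol Table 7 exempts symptomatic, not asymptomatic, short-lived Grade 3 biochemistry abnormalities, so read literally a silent MIRV-related AE can cost a MIRV dose level that its symptomatic equivalent does not

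*Protocol*

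**What the plan says.** Table 7 (Protocol Section 3.7.3.2) ends with a block for all other non-hematological toxicities. The block heading lists exceptions. One is "isolated symptomatic Grade 3 biochemistry laboratory abnormalities that last for" fewer than 7 days, and it continues "including electrolyte abnormalities that respond to medical intervention".

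A Grade 3 toxicity that is not excepted is held until it is Grade 1 or less, and MIRV then restarts one level down. The same cell has a separate instruction for a "Grade 3 ALT/AST increase": hold to Grade 1 or less, keep the dose if that takes no more than 7 days, and otherwise drop one level at the next cycle.

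Table 6 (Section 3.7.3.1) steps from 6.0 to 5.0 to 4.0 mg/kg AIBW and adds: "Reduction of MIRV below 4.0 mg/kg will not be permitted. Dose re-escalation is not permitted". The same section sets the general redosing criterion. "All non-hematologic toxicities for which a causal association to MIRV cannot be ruled out" must be Grade 2 or less or back to baseline, with tighter limits for ocular events and pneumonitis.

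Section 3.7.3 describes its content as "general guidance for AEs that are considered by the investigator to be possibly related or related to treatment with MIRV". Section 7.1.1 says: "An isolated, out-of-range laboratory result in the absence of any associated clinical finding may or may not be considered an AE".

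**The concern.** An exception for brief, isolated laboratory changes normally spares the patient who feels nothing. This one spares the patient with symptoms. Taken at its word, the less worrying event leads to a MIRV reduction that cannot be reversed, while the more worrying one escapes both the hold to Grade 1 and the reduction.

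The rule is operative. Section 3.2.2 tells sites to follow Section 3.7.3, and the sponsor has already revised the ALT/AST instruction in this same cell through a safety memo and an amendment. A reduction made on the literal reading would also enter the table of AEs leading to MIRV dose reduction planned in SAP Section 8.3. What is at stake is the MIRV dose some subjects receive, and consistent handling across sites.

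**Working it through.** The plan gives no figure to reproduce, so the check is one of rule logic.

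**Inputs.** The Table 7 heading exception, the general Grade 3 rule and the ALT/AST instruction (3.7.3.2); the dose steps, re-escalation bar and redosing criterion (3.7.3.1); scope (3.7.3); and the definition of an AE for laboratory values (7.1.1).

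**Literal outcomes** for a Grade 3 biochemistry abnormality lasting under 7 days that is classed as a MIRV-related AE:

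| Case | Symptoms | Exempt as written? | MIRV consequence |
|---|---|---|---|
| Not ALT/AST, not an electrolyte (e.g. bilirubin, creatinine) | No | No | Hold to Grade 1 or less, restart one level lower, no re-escalation |
| Same test | Yes | Yes | No reduction; redose at Grade 2 or less, or baseline |
| ALT/AST | Either | Own instruction | Hold; same dose if Grade 1 or less within 7 days |
| Electrolyte that responds to treatment | No | Unclear | Depends on whether *symptomatic* also limits the electrolyte clause |
| Electrolyte that responds to treatment | Yes | Yes | No reduction |

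Putting *asymptomatic* in the heading swaps the first two rows.

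**Size of one step.** (6.0 − 5.0) / 6.0 = 0.167, or 16.7% of the starting MIRV dose.

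**Direction of comparable rules:**

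- *Pneumonitis on MIRV (3.7.3.6):* "Subjects who are asymptomatic may continue dosing of MIRV with close monitoring". Lenient to the silent event.
- *Grade 3 laboratory values on SL-172154 (3.7.1.5):* the decision to hold rests partly on accompanying signs or symptoms. Lenient to the silent event.
- *Amylase/lipase in the DLT definition (3.5):* exempt only without clinical signs or symptoms or imaging evidence of pancreatitis. Lenient to the silent event.
- *General laboratory exemption in the DLT definition (3.5):* resolution within 72 hours, no symptom condition. Neutral.

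None of these favours the symptomatic event. Section 7.1.1 also uses *isolated* for a result without any clinical finding, and *isolated symptomatic* fits poorly with that usage.

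**The case against.** The strongest objection is that everything turns on one leading letter in a heading that appears once and has no counterpart in the SAP. There is no second copy to compare, and a letter lost in text conversion cannot be excluded. That stands, and it is why the fix begins with the source text.

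The comparison rules are also analogies: two are DLT criteria for SL-172154-related events, one governs SL-172154 dosing, and one concerns pneumonitis. None is a MIRV laboratory rule. That stands too. A reader might take it as established that *asymptomatic* was meant, but no section says so; it is a strong inference.

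Reach is narrow. Section 3.7 calls the guidelines non-prescriptive, and Section 3.2.2 also points to the MIRV IB or USPI. Section 7.1.1 lets the investigator decide that a silent laboratory value is not an AE, in which case Table 7 is never reached. All of this limits the harm. It does not make the instruction right for an event that is classed as a MIRV-related AE.

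Three stronger readings are tempting and are not supported:

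- *Every silent Grade 3 biochemistry abnormality costs a dose level.* ALT/AST has its own instruction, which does not depend on symptoms, and the electrolyte clause can be read as exempting treated electrolyte changes whatever the symptoms.
- *MIRV may be given through a symptomatic Grade 3 abnormality.* The redosing criterion still requires Grade 2 or less, or baseline, and accompanying symptoms that are themselves Grade 3 could fall under the same Grade 3 rule.
- *The recommended Phase 2 dose or a statistical result is compromised.* Nothing in the documents shows this.

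**Conclusion.** The point holds as a probable wording error in an operative dosing rule. For a MIRV-related Grade 3 biochemistry AE lasting under 7 days, other than ALT/AST and arguably other than electrolytes that respond to treatment, the heading as written reverses the expected leniency. The asymptomatic event takes a one-level reduction, 16.7% from the starting dose, without re-escalation; the symptomatic event does not.

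This rests on a literal reading, on the investigator classing the value as an AE at least possibly related to MIRV, and on the text being faithful to the source. The documents give no frequency for such events, so the overall effect cannot be quantified. No sample size, operating characteristic or planned analysis changes. The correction is still worth making, because it bears on patient dosing and no other section puts it right.

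**What to change.** Check the heading against the source text and confirm the intent with the clinical lead. If confirmed:

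1. Change *symptomatic* to *asymptomatic* in the Table 7 heading exception.
2. Add that Grade 3 ALT/AST increases continue to follow their own row. Without this, the corrected heading would exempt brief silent ALT/AST rises that the row says to hold. The same overlap exists today for symptomatic rises.
3. Leave the electrolyte clause inside the existing exception, with its limits of isolated, Grade 3 and under 7 days. Do not list it separately: the heading also governs the Grade 4 row, which requires permanent discontinuation, so a free-standing electrolyte exception could release Grade 4 or prolonged abnormalities from Table 7.

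The cost is a one-line edit carried in the next memo or amendment. Data collection and analysis do not change.

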3.7.3.3 Monitoring and Management of Nausea and Vomiting [MIRV Cohort]

MIRV-related nausea (46% all grades; 1% Grade ≥ 3) and vomiting (16% all grades; 1% Grade ≥ 3) have been reported in patients treated with MIRV, despite premedication with dexamethasone. Therefore, it is recommended that an antiemetic (e.g., 5-HT3 serotonin receptor antagonists such as palonosetron, granisetron, or ondansetron) medication is provided before each MIRV dose (Section 3.6). Additional antiemetics may be used at any time at the discretion of the investigator, according to institutional or other practice guidelines, ASCO, European Society for Medical Oncology (ESMO), and NCCN. Subjects should be advised to contact their treating physician at the first sign of vomiting or worsening nausea.

3.7.3.4 Monitoring and Management of Diarrhea [MIRV Cohort]

Mild to moderate diarrhea has been reported in subjects treated with MIRV. Subjects should be advised to contact the investigator at the first sign of diarrhea. Subjects may then be treated according to standard institutional practice. One suggested regimen would be the administration of loperamide 2 mg at the first sign of loose stool, with repeat dosing every two hours until symptoms resolve [Wadler, 1998].

3.7.3.5 Ocular Disorders [MIRV Cohort]

Changes in visual acuity resulting from reversible keratopathy have been reported in other studies of DM4-containing immunoconjugates that use the SPDB linker [Younes, 2012]. Subjects receiving MIRV in the Phase 1 and 3 trials (IMGN853-0401, IMGN853-0403) reported ocular AEs consistent with reversible keratopathy/corneal epitheliopathy. At the 6.0 mg/kg AIBW Q3W dose level, MIRV-related dry eye (26% all grades; 1% Grade ≥ 3), keratopathy (33% all grades; 1% Grade ≥ 3), blurred vision (42% all grades; 2% Grade ≥ 3), eye pain (13% all grades; 1% Grade ≥ 3), and photophobia (12% all grades; 1% Grade ≥ 3) were reported in Phase 3 study IMGN853-0403.

3.7.3.5.1 Monitoring and Preventive Measures [MIRV Cohort]

In early dose escalation there was a relationship observed between MIRV plasma exposure and likelihood of an ocular event as well as with response. Exposure-response modeling suggested that a dose of 6.0 mg/kg AIBW provided adequate exposure for response while also maintaining overall exposure within a range that decreased the potential for ocular AEs. Due to the observation of ocular disorders consistent with reversible keratopathy/corneal epitheliopathy in subjects treated with MIRV, ocular function will be carefully monitored. Ocular symptom assessments will be performed at baseline and at Day 1 of every cycle thereafter (Section 6.2).

A complete ophthalmic examination will be performed in all subjects receiving MIRV by an ophthalmologist, optometrist, physician assistant, or equivalent eye care professional and will include the following at a minimum: manifest refraction, best distance corrected visual acuity (BCVA), intra-ocular pressure (IOP) assessment, fundoscopy, and slit lamp examination to assess the cornea for keratopathy and other corneal abnormalities. The visual acuity assessment should be performed with refraction, rather than corrected or via pin hole. Fundoscopy is required at baseline and post-treatment visit (PTV) only.

- A complete ophthalmic examination will be performed in all subjects receiving MIRV at baseline (within 21 days before C1D1), prior to Day 1 dosing in Cycles 3, 5, and 7 and at

the PTV (\pm 2 weeks) including subjects who are asymptomatic or have \leq Grade 1 ocular AEs. Abnormal corneal findings in asymptomatic subjects will be managed as per [Table 8](#).

- Subjects receiving MIRV who experience CTCAE $>$ Grade 1 ocular AEs while on study will have a complete ophthalmologic examination performed at the emergence of symptoms and at every other cycle thereafter until resolved to baseline or deemed irreversible in the opinion of the eye care professional. Subjects requiring an ophthalmological examination due to symptoms prior to Cycle 2 or 4 will then proceed to every other cycle (approximately 6 weeks) exams as indicated by findings and do not require the routine, asymptomatic exams at Cycle 3, 5, and 7.

Subjects are advised to avoid using contact lenses while on MIRV except when benefit outweighs risk per an eye care professional. Eyelid hygiene should be performed as per direction of an eye care professional. Please refer to Section [5.3.2.2](#) for details on the use of lubricating artificial tears and recommendations for prophylactic steroid eye drops in subjects with ocular symptoms. The use of UVA/UVB sunglasses in full daylight is recommended during the study. If subjects report signs or symptoms of ocular AEs, including but not limited to blurred vision or eye irritation, the management and dose modification guidelines outlined in [Table 8](#) and [Table 9](#) should be followed.

3.7.3.5.2 Management and Dose Modifications Guidelines [MIRV Cohort]

If a subject develops new CTCAE $>$ Grade 1 ocular symptoms, MIRV will be held until the subject undergoes a complete examination by an eye care professional. If a subject is found to have confluent superficial keratitis, a cornea epithelial defect, or a 3-line or more loss in BCVA, MIRV dosing must be interrupted until findings improve to nonconfluent keratitis, prior baseline, or complete resolution. Uveitis must improve to Grade 1 or better or prior baseline. Treatment with MIRV may resume if the ocular event improves as above within 28 days of the next scheduled MIRV dose (refer to [Table 8](#) and [Table 9](#) for details). Corneal AEs of any severity should be followed to complete resolution, pretreatment baseline, or are deemed to be irreversible according to the eye care professional. For 2 or more overlapping ocular adverse events (ocular disorders/corneal adverse reactions), dose modification should be based on the ocular adverse event of greater severity. Any other ocular AEs not specifically noted in [Table 8](#) or [Table 9](#) will be managed at the discretion of the treating physician in consultation with their eye care professional.

Subsequent eye examinations will be scheduled to occur in every other cycle going forward from the time that the corneal AE was initially reported until resolution of the corneal toxicity to subject's prior baseline or complete resolution or until it is deemed irreversible even if the results of the subject's ocular symptom assessment show no obvious clinical findings. For subjects with ongoing keratitis/keratopathy, a cornea epithelial defect, or a 3-line or more loss in BCVA at the PTV, an ophthalmic examination should be done every 30 days until complete resolution, stabilization without likelihood of improvement in the opinion of the eye care professional, or return to pretreatment baseline. Ocular symptoms (e.g., blurred vision) should also be assessed at this time. The visual acuity assessment should be performed with refraction, rather than corrected or via pin hole. Refraction is crucial for cases where subjects report blurred vision or other ocular AEs.

Management of ocular AEs with inflammatory characteristics or other non-corneal/visual acuity ocular AEs should include measures as indicated by an eye care professional.

Recommended dosage modifications for corneal AEs should be based on both corneal examination findings using the system outlined in [Table 8](#) and changes in BCVA. Dose modifications for non-corneal ocular AEs are at the discretion of the treating physician, in collaboration with an eye care professional.

Note: [Table 8](#) describes the management of corneal adverse reactions with regard to MIRV dosing. See [Table 15](#) and [Table 16](#) in Appendix Section [16.6](#) for grading of ocular AEs.

Table 8 Management of Corneal Adverse Reactions (Keratitis/Keratopathy)

Ocular Exam Finding ^a	Management	Guidelines for MIRV Dose Modification
Nonconfluent superficial keratitis or nonconfluent keratopathy ^b	Complete eye examination as outlined in SOA (Section 6.2). Subjects should have frequent symptomatic ocular assessments and repeat eye examinations at least every 6 weeks until resolved to pretreatment baseline or nonconfluent superficial keratitis or better or are deemed to be irreversible by the investigator, even after treatment discontinuation, if needed	Monitor with scheduled ocular exam to complete resolution or return to pretreatment baseline. Continue MIRV dosing.
Confluent superficial keratitis or confluent keratopathy ^b , cornea epithelial defect (+NaFl staining), or \geq 3-line loss in BCVA	Complete eye examination as outlined in SOA (Section 6.2). Subjects should have weekly symptomatic ocular assessments and repeat eye examinations at least every 6 weeks until resolved to pretreatment baseline or are deemed to be irreversible by the investigator, even after treatment discontinuation, if needed.	Hold MIRV dosing until AE has resolved to pretreatment baseline or nonconfluent superficial keratitis or better. Subjects with corneal adverse reactions lasting $<$ 14 days may be allowed to resume MIRV at the same dose level. Recurrence of toxicity on subsequent cycles despite best supportive care will require a dose reduction to one lower dose level. Subjects with corneal adverse reactions lasting \geq 14 days but no more than 28 days may resume MIRV at one lower dose level. If findings persist $>$ 28 days, continuation at reduced dose level is at the discretion of the investigator in consultation with the Sponsor.
Corneal ulcer or clinically significant stromal opacity or BCVA 20/200 or worse	Complete eye examination as outlined in SOA (Section 6.2). Subjects should have weekly symptomatic ocular assessments and repeat eye examinations at least	Hold MIRV dosing. Subjects may be allowed to resume MIRV at one lower dose level after AE has resolved to

Ocular Exam Finding ^a	Management	Guidelines for MIRV Dose Modification
	every 6 weeks until resolved to baseline or are deemed to be irreversible by the investigator, even after treatment discontinuation, if needed.	nonconfluent keratitis or better or to pretreatment baseline within 28 days. If findings persist >28 days, continuation at reduced dose level is at the discretion of the investigator in consultation with the Sponsor.
Corneal perforation	Complete eye examination as outlined in SOA (Section 6.2). Subjects should have weekly symptomatic ocular assessments and repeat eye examinations at least every 6 weeks until resolved to baseline or are deemed to be irreversible by the investigator, even after treatment discontinuation, if needed.	Permanently discontinue MIRV dosing.

^a Normal = clear cornea, no epithelial defects.

^b Nonconfluent microcystic epithelial change, punctate epithelial keratopathy, subepithelial inclusion cyst and/or nonconfluent superficial keratitis, superficial punctate keratitis, epithelial erosion

Table 9 Management of Ocular Disorders

Refer to [Table 8](#) for Corneal Adverse Reactions.

Severity Grade (CTCAE v5.0)	Management	Guidelines for MIRV Dose Modifications
Grade 1	Follow SOA (Section 6.2) Monitor for worsening symptoms	Continue MIRV dosing
Grade 2	Complete eye exam as outlined in SOA (Section 6.2) Repeat complete exam as clinically indicated. Subjects should have weekly symptomatic ocular assessments by the investigator until the symptoms resolve to Grade \leq 1 or are deemed to be irreversible by the investigator.	Hold MIRV dosing until AE has resolved to Grade 1 or better. Subjects with ocular symptoms lasting < 14 days may be allowed to resume MIRV at the same dose level. Subjects with ocular symptoms lasting \geq 14 days but no more than 28 days may resume MIRV at one lower dose level. Recurrence of Grade 2 toxicity on subsequent cycles despite best supportive care will require a MIRV dose reduction of one dose level.
Grade 3	Complete eye exam as outlined in SOA (Section 6.2). Repeat complete exam as clinically indicated. Subjects should have weekly symptomatic ocular assessments by the investigator until the symptoms resolve	Hold MIRV dosing. Subjects may be allowed to resume MIRV at a lower dose after AE has resolved to Grade 1 or better within 28 days. Recurrence of Grade 3 toxicity on subsequent cycles despite best supportive care will require a MIRV dose reduction of one dose level.

Severity Grade (CTCAE v5.0)	Management	Guidelines for MIRV Dose Modifications
	to Grade \leq 1 or are deemed to be irreversible by the investigator.	
Grade 4	Complete eye exam as outlined in SOA (Section 6.2). Repeat complete exam as clinically indicated. Subjects should have weekly symptomatic ocular assessments by the investigator until the symptoms resolve to Grade \leq 1 or are deemed irreversible by the investigator.	Permanently discontinue MIRV.

